## **OBJECTIVES/AIMS/HYPOTHESES**

The objective of this randomized control clinical trial is to provide data on the clinical impact of neurofeedback (NFB) treatment OEF-OIF-Operation New Dawn (OND) Veterans diagnosed with mTBI and experiencing persistent post-concussive symptoms as compared to a randomized control group, who will only receive usual care. Comparisons will be made at baseline, at the study treatment midpoint (around 4-6 weeks), and conclusion of study treatment (around 8-10 weeks) and at a two-month follow-up. The effect of NFB will be assessed on the following:

1. Frequency of headaches as measured by NEUROQOLTBI headache tool, and headache impact on functioning as measured by Headache Impact Tool (HIT-6)
2. Severity of sleep disturbance as measured by Insomnia Severity Index (ISI) and quality of sleep as measured by the NEUROQOLTBI Sleep disturbance tool.
3. Attentional functioning as measured by computerized visual attention performance test (QIKTest) accuracy index
4. Quality of life as measured by Quality of Life after Brain Injury (QOLABI) and NEUROQOLTBI Satisfaction with roles and activities & Ability to Participate in roles and activities.
5. General physical and emotional symptoms possibly co-occurring with mTBI as measured by self-report using General Symptom Scale (GSI), Depression, Anxiety and Stress Scale (DASS21), Post-Traumatic Stress Disorder Checklist (PCL), Patient Health Questionnaire-Depression (PHQ9), and NEUROQOLTBI Positive affect and wellbeing short form.

We aim to conduct a full-scale trial to determine whether NFB is a clinically relevant intervention in the care OEF-OIF-OND Veterans with mTBI who are experiencing chronic symptoms of headaches, insomnia and attention difficulties.

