## **Hypotheses**

We hypothesize that the intervention group, receiving NFB training over the course of treatment, relative to the control group, will experience a clinically and statistically significant change in scores that indicates:

1. decreased severity of headaches on the NEUROQOLTBI headache tool and enhanced functioning on the HIT-6.
2. greater improvement in perceptions of quality of sleep on the NEUROQOLTBI Sleep disturbance tool and decreased severity of sleep disturbance on the ISI.
3. greater improvement in attention function in the QIKTEST accuracy index.
4. greater improvement in quality of life as shown by enhanced involvement in roles on the NEUROQOLTBI Satisfaction with roles and activities & Ability to Participate in roles and activities tools and on the QOLATBI baseline scores.
5. greater improvement in general physical and emotional symptoms score on the PCL-5; on the PHQ9; on the DASS21; on the GSI, and on the NEUROQOLTBI Positive affect and wellbeing tool

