
cosigned by a research team member for verification purposes. If the gift card(s) is mailed, staff will send the gift card(s) using a return receipt method (e.g., certified mail) to ensure delivery to the participant. A letter will be included with the mailing. The letter will list the visit date(s) and type (e.g., assessment, treatment) associated with the gift card(s). Staff will maintain contact with the participant (e.g., phone call advising of mailing date) to help ensure successful delivery. The return receipt will be filed with the participant's study chart. If the gift card(s) is delivered electronically, the message will include a table with a list of the visit date(s) and type (e.g., assessment, treatment) associated with the gift card(s). The message will ask the participant to reply to the message to acknowledge receipt of the gift card(s). The message will be saved and filed with the participant's study chart.

In addition, interventions will be offered at hours and days that would enable Veterans who work to participate. Phone calls will be made as session reminders, the week and day before as well as on the day of appointment. In addition, a paper monthly calendar with the appointments indicated that can be hung on the wall will be given as well as an appointment card at the end of each session. In addition, those in the control group, will be offered NFB training, after they complete the control group requirements.

**Outcome Measures:** Outcome measures will be used to compare the results of the NFB intervention and control group. Statistical tests and analyses will be conducted to determine the existence of statistical differences between the intervention and control group measures and on the measures at pre-treatment, midpoint, and immediate post treatment for determination of clinical improvement.

To determine the impact of NFB, the following assessment tools (see Table 4) will be administered at baseline, 4-6 weeks (midpoint of treatment), and 8-10 weeks (conclusion of treatment) and 2 months following completion to the control and intervention mTBI groups.

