## Statistical and Data Analysis Plan

The analyses will be conducted based on intention-to-treat principle (Friedman, Furberg, DeMets, 2010) where participants are analyzed according to their group assignment regardless of the treatment received (e.g., switching treatments or poorly adhering to assigned treatment). Patient demographics will be presented using frequencies and percentages for categorical variables and means and standard deviations for continuous variables. Although balance between intervention arms will be guaranteed by randomization, there may be unmeasured confounding. Two sample t tests or chi-square tests will be conducted to investigate potential confounding effects on demographic variables.

For each hypothesis, first two sample t-tests will be utilized to assess the effect of NFB intervention at each time. Then, a repeated-measures analysis of variance (ANOVA) will be implemented for the outcome variable that shows significant group effect. The mixed effects model will include group (between-factor), time (within-factor), and the interaction between group and time as fixed effects. From this model, the interaction will allow the testing of whether longitudinal trajectory is associated with group assignment. The longitudinal trajectory from baseline, 4-6-week and 8-10-week to 2-month follow-up, for each outcome of interest will be investigated in this model accounting for covariance structure (e.g., AR(1)) within participants. This determines the rate of improvement during the course of the intervention. Any baseline subject characteristics found to differ between groups as covariates to assess the impact of the baseline covariates on the effectiveness of the intervention over the course of the study will also be included if needed].

The outcomes of interest for each hypothesis are clinically significant:

- 1) Reduction in frequency, severity and/or impact of headaches: HIT-6 and NEUROQOLTBI
- 2) Improvement of perceptions of quality of sleep and insomnia severity: ISI and NEUROQOLTBI Sleep disturbance
- 3) Improvement in attention function: QIK-Test
- 4) Improvement in the quality of life: QOLIABRI and NEUROQOLTBI Satisfaction & Participation in roles and activities

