## 5) Improvement in the general physical and emotional symptoms: GSI, DASS21, PHQ9, PSL-5 and NEUROQOLTB Positive affect and wellbeing.

As a secondary analysis, a per-protocol analysis will investigate the effect of the intervention in participants that adequately adhere to the intervention, e.g., participants that attend over half of the treatment sessions versus participants attend less half of the treatment sessions. For all analyses, model assumptions will be evaluated with graphical and formal statistical tests such as Kolmogorov-Smirnov goodness-of-fit test. If there is marked nonlinearity or non-normality, transformation of the dependent variable or using a different link function such as the log link function will be considered. All analyses will be done in SAS version 9.4 on a non-VA Computer with two-tailed tests and P-value < 0.05 will be considered statistically significant.

Other statistical analyses not run by the biostatistician will be completed by the research team within the VA Informatics and Computing Infrastructure (VINCI) workspace.

**Power:** Power: Literature on NBF studies of patients with TBI have reported dropout rates ranging from 10% to 30% (Nelson & Esty, 2012; Zoeful, Huster, & Herrmann, 2011). Assuming a dropout rate of 28% and a moderate autocorrelation of 0.6 among repeated measures, this sample size will ensure to detect at least significant difference of 0.49 standard deviation with a power of 80% in the NFB intervention group compared to the control group with two-tailed significance level of 0.05 based on Diggle's et al (2002) approach for 4 repeated measures. This indicates that differences of less than 15% can be detected for HIT-6 (5.8% based on Cerritelli, 2015) and QOLABRI (13.8% based von Steinbuechel et al, 2016) and less than 26% for ISI (17.9% based on Nguyen, 2017) and DASS21 (19.7% based on Arundine et al., 2012) questionnaires. Thus, differences of 15% to 25% in the study instruments would be clinically significant. In addition, this study will detect a difference of at least 0.67 standard deviation if multiple testing is adjusted using FDR, which also provides a moderate effect size.

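### Thirteen outcomes are t-tested at each visit at an unadjusted 5% level, no outcome or visit is primary, and the FDR adjustment is mentioned but never adopted

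*Combined protocol and SAP*

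**What the plan says.** The Hypotheses section and the Statistical and Data Analysis Plan list the same 13 outcomes under five hypotheses:

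- H1, headache: HIT-6 and NEUROQOLTBI headache.
- H2, sleep: ISI and NEUROQOLTBI sleep.
- H3, attention: QIKtest.
- H4, quality of life: the quality-of-life-after-brain-injury scale and two NEUROQOLTBI role scales.
- H5, general symptoms: GSI, DASS21, PHQ-9, PCL-5 and NEUROQOLTBI positive affect.

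None is ranked above another. The word secondary is attached only to the per-protocol analysis.

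For each hypothesis, "first two sample t-tests will be utilized to assess the effect of NFB intervention at each time". A repeated-measures model with a group-by-time interaction then "will be implemented for the outcome variable that shows significant group effect". For all analyses, "two-tailed tests and P-value < 0.05 will be considered statistically significant".

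Multiplicity is mentioned once, in the Power paragraph: "this study will detect a difference of at least 0.67 standard deviation if multiple testing is adjusted using FDR". No level, family of tests or contrast goes with it.

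The visits also differ by section. The Objectives compare the arms at baseline, "at the study treatment midpoint (around 4-6 weeks), and conclusion of study treatment (around 8-10 weeks) and at a two-month follow-up". The Outcome Measures paragraph refers to "pre-treatment, midpoint, and immediate post treatment for determination of clinical improvement" and leaves out the follow-up.

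**The concern.** With several scales and visits per hypothesis, each tested at the full 5% level, a treatment that does nothing has more than the nominal 2.5% chance of a significant result in its favour. The plan does not say whether a hypothesis is decided by one visit t-test, by all its measures together, or by the interaction. It also does not say whether the 5% rule applies to raw or FDR-adjusted p-values.

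The trial is meant to show whether neurofeedback is clinically relevant for these Veterans. A reader of the results could not tell which comparison was the intended test of a hypothesis, or whether an FDR correction had been planned or was added once results were known. The screen does not cure this, because it admits outcomes to the model on the strength of an unadjusted result.

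**Working it through.** **Count of tests.** Outcomes: 2 + 2 + 1 + 3 + 5 = 13. Three post-baseline visits give 13 × 3 = 39. If baseline counts as a visit, 13 × 4 = 52. With only midpoint and end of treatment, as in Outcome Measures, 13 × 2 = 26.

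**False-positive rates.** Inputs from the documents are 36 completers per arm (Accessible Population and Methods of Recruitment), correlation 0.6 between repeated measures (Power), and two-tailed 0.05. The documents give no correlation between outcomes, so 0 to 0.8 is assumed. Simulated trials with no effect give the chance of at least one significant t-test favouring neurofeedback:

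| Hypothesis | Outcomes | Tests | Chance |
|---|---|---|---|
| H1 headache | 2 | 6 | 9–12% |
| H2 sleep | 2 | 6 | 9–12% |
| H3 attention | 1 | 3 | 6% |
| H4 quality of life | 3 | 9 | 11–17% |
| H5 general symptoms | 5 | 15 | 14–26% |
| All | 13 | 39 | 20–54% |

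The upper ends can be checked by hand. One outcome over three visits gives about 12% in either direction, so about 6% in favour. With uncorrelated outcomes:

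- two outcomes: 1 − 0.94² = 12%
- three outcomes: 1 − 0.94³ = 17%
- five outcomes: 1 − 0.94⁵ = 27%
- thirteen outcomes: 1 − 0.94¹³ = 55%

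These use exchangeable visit correlation; over all 39 tests, AR(1) changes the rate by no more than about three points. Dropping the follow-up (26 tests) gives about 16% to 45% over all outcomes.

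**Stricter readings, over all five hypotheses.** If every measure of a hypothesis must succeed at one visit, the chance of at least one favourable hypothesis is 7–8%. Most of that comes from H3, which has a single measure; without it the figure is 0.3–5%. If a favourable t-test and a significant interaction are both needed, it is 5–13%.

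**The plan's detectable differences.** For the average of four measures with 36 per arm, SE = √[2(1 + 3 × 0.6)/(4 × 36)] = 0.1972 SD.

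- Two-sided 0.05: (1.960 + 0.842) × 0.1972 = 0.552, not the stated 0.49.
- One-sided 0.05: (1.645 + 0.842) × 0.1972 = 0.490. This matches the figure but not the stated two-tailed level.
- The FDR figure of 0.67, taken at the strictest step, fits about 5 tests two-sided (0.674), about 9 to 10 one-sided, or about 18 if 0.49 is rescaled two-sided. The family behind it cannot be recovered.

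**Detectable difference for one baseline-adjusted contrast at end of treatment**, at 80% power. The 13 Benjamini-Hochberg steps run from 0.05 down to 0.05/13 = 0.0038 (z = 2.890).

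- Exchangeable: SE = √[2(1 − 0.6²)/36] = 0.1886, giving 0.53 to 0.70 SD.
- AR(1), end of treatment two steps from baseline (0.6² = 0.36): SE = √[2(1 − 0.36²)/36] = 0.2199, giving 0.62 to 0.82 SD.

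For comparison, an unadjusted single-visit t-test at 0.05 has SE = √(2/36) = 0.2357 and detects 0.66 SD.

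**The case against.** The strongest reply is that the rate over all 39 tests presumes a rule the plan never states. A reader might infer that one favourable result among the 39 would count as trial success. The documents do not say so: they set out five separate hypotheses and analyse each one. That stands, and it is why the per-hypothesis rates are the main measure here. They are lower, but every one still exceeds 2.5%.

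The stricter readings also have support in the text. The Hypotheses section joins measures with "and" and says the intervention group "will experience a clinically and statistically significant change in scores that indicates"; the analysis plan puts the interaction model after the t-tests. Neither is written as the decision rule, and the headache outcome in the analysis plan is worded with and/or. So the rule is ambiguous, and the size of the inflation depends on how it is read.

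A reader might also infer that 0.67 SD reveals a planned five-test family, one per hypothesis. It does not. The formula behind that match fails to return the plan's own 0.49, and other conventions give other counts.

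Finally, a primary outcome or a fixed hierarchy would also answer the concern, and Benjamini-Hochberg does not bound the chance of any false positive. Both remarks are fair. FDR is proposed because the plan already names it, and its limit has to be stated.

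**Conclusion.** The concern holds. As written, the plan tests 13 equally ranked outcomes at each visit without adjustment, names no deciding outcome, visit or test, and adopts no multiplicity method. With no true effect, the chance of a favourable significant t-test is about 6% for the single-measure attention hypothesis, rising to 14–26% for the five-measure hypothesis, against 2.5%. Over all 39 tests it is 20–54%. Roughly 5–13% applies over the whole set under stricter rules that the text hints at but does not set.

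These figures assume 36 per arm, visit correlation 0.6 and between-outcome correlation of 0 to 0.8; only the last is not from the documents. This is more than a missing detail, since following the stated rule produces the inflation. What counts as a clinically significant change is a separate question and is not part of this point.

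**What to change.** In the Statistical and Data Analysis Plan, including its Power paragraph:

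1. Fit the repeated-measures model to all 13 outcomes and remove the t-test screen.
2. Make the baseline-adjusted group difference at end of treatment the single deciding contrast for each outcome. Treat the other visits and the interaction as supportive.
3. Commit to the FDR adjustment already mentioned: Benjamini-Hochberg at 5% across the 13 contrasts. State that it controls the false discovery rate, not the chance of any false positive. In simulation, the latter was about 3–5% with no effect on any outcome. It was 7–18% when 6 of the 13 responded at an assumed 0.9 SD, with the false discovery rate at 2–3%.
4. Date the rule before any comparison by arm, or disclose it as post hoc. The Data Protection section indicates that work with participants had ended by March 2025, so the sponsor should confirm in writing whether outcomes have already been compared.
5. Replace 0.67 SD with the detectable difference for this family and contrast: about 0.53–0.70 SD (exchangeable) or 0.62–0.82 SD (AR(1)) at 36 per arm.

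The cost is SAP wording and that dated confirmation; no new data are needed. The downside is lower power for any single scale, partly offset by the baseline adjustment.

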### **Potential Benefits to Participants:**

The benefits to the subject could include: For the participants receiving NFB, benefits may include a decrease in the number and severity of headaches, enhanced sleep, and attention ability and an overall perception of enhanced quality of life. In addition, the participant may experience enhanced positive emotions. Indirect benefits include the knowledge that the participant has contributed to the body of knowledge relating to the efficacy of NFB. There may be no direct benefit to volunteers.

**Risk-Benefit Ratio:** The risks of this project are designed to be minimal, and there are several safeguards in place that will minimize any associated risks related to this study.

### **Potential Risks to Participants:**

The risk to volunteers in this study is designed to be minimal. Because this intervention is a personal biofeedback process, whereby the participants are training themselves based on their own physiological parameters, no serious adverse event is anticipated or expected. Anticipated and not serious brief side effects such as anxiety, a tightness in muscles, stomach discomfort, or mental cloudiness may be experienced but are expected to go away within minutes. Most people feel relaxed and calm during and after NFB training.

As mentioned earlier, each person has a particular setting on the equipment that the person's brain prefers. Until the NFB specialist finds that particular setting, although unlikely, it may be possible that some symptoms may feel a little worse when the individual goes home or the next day. This is not bad news since it informs the NFB specialist more about a person's brain and the particular setting that a brain prefers can be found more quickly. The NFB specialist can always find that setting especially with the individual's help by letting the NFB specialist know how they are feeling. In very little time, a NFB specialist can find that setting, and any symptoms the individual was experiencing before the study may begin to get better. If this occurs at all, it is usually very short-term, not usually more than a minor discomfort, and easily adjusted.

Although some adverse events have been published in the literature relating to NFB, they were either related to a study involving the use of arbitrary non-individualized settings (essentially using sham techniques) (Rogel et al, 2015) or an article that outlined off-hand comments made by a few practitioners on list groups who were seeking guidance from other practitioners about issues experienced while conducting NFB. The practitioners themselves were not informed that their comments were to be published. The actual skill or previous training of these practitioners was not indicated, nor were there case-studies of the patients or protocols discussed

(Hammond & Kirk, 2007). Although no adverse events were ever experienced in the private practice of the PI, any unexpected or serious adverse events will be reported to the VAPIHCS IRB. The event will be categorized (mild, moderate or severe) with its relationship to the study indicated (e.g. definitely related, probably related, possibly related, unlikely related, unrelated). The investigators will evaluate each adverse event. Any adverse event previously documented will be recorded as “ongoing,” “improved,” “resolved” or “worsened” as appropriate. If an adverse event changes, or advances in quantity or quality, a new IRB report and record of the event will be initiated and the old adverse event will be ended.

**Risk Level:** The study is designed to have a risk level of minimal, in that the probability and magnitude of harm or discomfort anticipated in the research is not greater than that ordinarily encountered in daily life or during the performance of routine physical activity or psychological examinations or tests.

**Physical Risks:** We do not anticipate any risk of physical harm as a result of participating in the study.

**Risk of Emotional Upset:** The risks of the proposed study are believed to be minimal. Some participants might experience some concern about anonymity. The research team will be available during or after the data collection to answer address any concerns a participant might have regarding this issue and strong data safety procedures are being implemented to protect participants’ anonymity.

**Social, Legal, and Economic Risks:** The study does not discuss information on protected topics. Participants will not be personally identified in any reports or publications that may result from this study.

**Financial Obligation:** There will be no cost to participants for any treatment received as part of this research study. Some Veterans are required to pay a co-payment for medical care services provided by the VA. This co-payment requirement will continue to apply to medical care and services provided by the VA or community provider that are not a part of this study.

**Therapeutic Risk and Research Risk:** There are no known research risks in this study. It is a training biofeedback program.

**Vulnerable populations:** There is a possibility that a Veteran who may be economically disadvantaged may be enrolled. However, because this study offers no financial incentives, there is no financial coercion that would require additional safeguards for the economically disadvantaged. Additionally, the economically disadvantaged is not a group that is targeted for this study. If a woman becomes pregnant while participating in this study, she will be removed from active engagement with an intervention but will be followed through the course of the study and will complete the assessments.

